#### Statistical Analysis Plan

Participant data were extracted and stored on password protected Microsoft Excel spreadsheets on university computers. Data was reduced using the mean value of the 5 trials for each variable in each testing session was calculated, resulting in 5 values for each variable (except fatigue) and each participant used for statistical analysis. The fatigue scores were a numerical value between 0-20 and only collected twice, pre and post all sessions, resulting in 2 values for each participant. Data collected from their Novi Survey and in their first session were collated and summarised into mean, range and dispersion values for their anthropometric and MS data. Analysis was carried out on SPSS (version 23) using mean values with standard error dispersion values. All dependent variables for muscle response, single stance balance, sit-to-stand stability, pain, and fatigue scores were analysed each in a between-subjects repeated measures ANOVA. This was to determine differences between the two treatment groups and between the different time points.

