## Study Protocol

### Participants

20 participants were recruited for this study in a mixed factor study design. The recommended number of participants for repeated measures, between factors ANOVA is 36 (18 participants in each group). This was shown from a G-power calculation with a large effect size (0.4), a power of 0.8 and a significance level of 0.05. Due to time constraints, participant availability and feasibility, recruitment and data collection was completed after 20 participants. Participants were recruited via posters, social media, word of mouth and contacts made with multiple sclerosis (MS) therapy centres.

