### Procedure

If interest was shown, an information sheet with inclusion and exclusion criteria was given to the participant and a link to a Novi Survey to gather information about their MS and health condition. Only the main researcher had access to this information on the Novi Survey. All participant information was pseudonymised according to their participant number. If the participant was eligible, they were randomly allocated to group A or group B by a random group generator on Microsoft ExcelTM, to organise suitable times for their sessions. Group A received a general massage for four sessions and group B received the mobilisation intervention for four sessions.

Participants were required to attend on four separate occasions, receiving the same treatment for each session. Though previous studies have recommended more sessions from their results, the time constraints on this project did not allow for more than four sessions per participant. Four sessions would still allow analysis for a cumulative effect, however previous research would indicate that eight - twelve sessions is more likely to show benefit from a manual therapeutic intervention. This was a single-blind trial, so participants were blind as to which treatment they were receiving. All testing took place at the Edinburgh Napier University Sighthill campus Engage building in a physiotherapy room which was maintained at standard room temperature (20-25°). The participants were asked to attend sessions at the same time on four consecutive weeks, to have a consistent gap between sessions.

Upon arrival, participants had the opportunity to read through the information sheet again and the researcher ran through the protocol with each participant. Participants were invited to ask any questions about the study before consent forms were given and encouraged to ask throughout the sessions if they wanted. They were informed they could withdraw from the study at any point and it would not affect their treatment. Their data could be removed up until the point of dissemination of summarised results. Once written consent was given, anthropometric measures were taken for age, weight, and height. Information was also taken regarding their most prominent symptoms and location of symptoms. Results from their Novi Survey were reviewed to go through their MS condition and Expanded Disability Status score.

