#### Outcome Measures

Participants self-reported pain using a visual analogue scale (VAS). The VAS uses a pain rating scale from 0-10, 0 represented no pain and 10 represented worst pain felt. Participants were given a visual scale to rate their resting lower back pain in each of the testing sessions.

Participants completed a shortened version of the Modified Fatigue Impact Scale consisting of five questions on the impact of fatigue in their lives over the past 4 weeks. There was a total possible score of 20. This was completed at the start of the first session and at the end of the fourth session.

Myometer tests were completed using a myometer palpation device (MyotonPRO, Myoton Ltd., London UK). This previously validated handheld device has been documented to give reliable results for muscle stiffness, tone and elasticity. The myometer is a form of indenter and the main form of measuring viscoelastic properties of tissue. The indenter is placed above the desired tissue and produces a series of short force impulses from the electromagnetically activated device. This causes small deformations in the tissue for a predetermined period, to which the tissue responds with damped oscillations determined by its viscoelastic properties. These oscillations are recorded by an accelerometer on the testing end of the indenter, recording the muscle deformation characteristics via an acceleration signal. Stiffness is calculated as the ratio of resisting force response and the change in length of the tissue, tone is calculated as responding tissue acceleration signal frequency and elasticity is calculated as the logarithm decrement of the acceleration signal dampening frequency (the natural log of the ratio of two successive the acceleration signal peaks). The stiffness, tone and elasticity parameters are reported as a mean of these impulses along with a coefficient of variation (CV). Values were only accepted if the CV was less than 3%, complying with the manufacturer recommendations.

Measurements were collected on both sides of erector spinae muscle and using the higher mean value to determine the stiffer side of the spine for treatment. Measurements were taken from the central belly of this muscle by asking the participant to lift their head and feet

at the same time, contracting their back muscles to allow for muscle belly palpation. This spot was then marked and measured.

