The participants then performed two balance tests positioned on the force plates. Test one involved a single leg stance test, collecting measurements for body sway total path length, anterior-posterior path length, medial-lateral path length and velocity using the tracked centre of pressure recording. The second test used was a sit-to-stand test. This required a calibration of force plates to the participant's body weight. Participants were seated on a chair directly in front of the force plate, with their feet resting on the force plate. They were asked to move from a sit to stand position, using only their leg strength. This was repeated five times. The researcher was available to help at any time if participants felt uncomfortable or unstable during the tests or therapy session. Participants were encouraged to rest between the balance tests or at any time they felt tired.

The software used to collect the force data (Kistler, MARS) gave an automatic output for the variables used in analysis. These were centre of pressure body sway velocity, rising index (the percentage of body weight applied to the force plates during the standing movement) and weight transfer (the time taken to stand). A total of five testing sessions were completed for each participant, pre and post session one, and post sessions two, three and four.

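### The repeated measures ANOVA names no sphericity correction and treats the pre-treatment value as an outcome time, which risks excess type I error and dilutes the treatment comparison

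*Combined protocol and SAP*

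**What the plan says.** The Statistical Analysis Plan section gives one method for all outcomes: each is "analysed each in a between-subjects repeated measures ANOVA". Its stated aim is: "This was to determine differences between the two treatment groups and between the different time points". The group-by-time interaction is not named. On execution it says only: "Analysis was carried out on SPSS (version 23) using mean values with standard error dispersion values". There is no sphericity check, no epsilon correction, no rule for missing values and no role for baseline as a covariate.

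Under Outcome Measures, the test occasions are "pre and post session one, and post sessions two, three and four". The Procedure section puts the sessions in consecutive weeks, so the first two tests share a day and the others follow weekly. All five values enter the analysis, so the pre-session-1 value is an outcome time like any other. Fatigue has two values only.

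The Participants section bases the sample size on "a large effect size (0.4), a power of 0.8 and a significance level of 0.05". This gave 36 participants; recruitment ended at 20.

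**The concern.** Two features of the model matter.

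- **Sphericity.** The within-subject F tests (time, group-by-time) hold their nominal level only if all pairwise differences between times have equal variance. Two readings either side of one 30-minute treatment would usually correlate more closely than readings three weeks apart. If so, uncorrected tests reject too often. The five test occasions are there to look for a cumulative effect, and a cumulative effect that differs between groups is the group-by-time term. Because the plan does not say whether a corrected result will be reported, that choice remains open after the results are seen.
- **Baseline as an outcome.** Treatment cannot affect the pre-session-1 value. Averaging it into the group effect pulls the estimated difference towards zero, and its value as a predictor of later readings goes unused. With 20 participants against a stated 36, there is little power to spare.

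A third feature is conditional: this ANOVA drops any participant who lacks one of the five values.

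**Working it through.** **Inputs.** From the documents: 20 participants, five test times, effect size f = 0.4, alpha 0.05. Assumed: 10 per group (the split is not stated), SD 1 at each time, and the correlations given below. For two equal groups f = d/2, so f = 0.4 is a difference of 0.8 SD.

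**The plan's own figure.** For the between-factors test, lambda = f²Nm/(1+(m-1)ρ) on 1 and N-2 df. The number of measurements m and correlation ρ are not given.
- With m = 5, ρ = 0.6, N = 36: lambda = 0.16×36×5/3.4 = 8.47, power 0.807. The stated 36 is reproduced. It is also reproduced with m = 3, ρ = 0.5; with m = 5, ρ = 0.5 the answer is 32.
- With m = 5, ρ = 0.6, N = 20: lambda = 0.16×20×5/3.4 = 4.71, power 0.54.

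This formula places the 0.8 SD difference on the average of all the times, including the pre-treatment one if m = 5.

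**Power when the effect exists only after treatment** (0 at baseline, 0.8 SD at each later time, ρ = 0.6 throughout, 10 per group):
1. Group main effect. Mean difference over five times = 0.8×4/5 = 0.64. SD of a five-time mean = sqrt((1+4×0.6)/5) = 0.825. Noncentrality = (0.64/0.825)×sqrt(5) = 1.74 on 18 df. Power 38%.
2. Group-by-time. Sum of squared deviations of the difference from its mean = 0.64² + 4×0.16² = 0.512. Lambda = 5×0.512/(1-0.6) = 6.4 on 4 and 72 df. Power 47%.
3. Post-treatment mean adjusted for baseline. Residual SD = sqrt((1+3×0.6)/4 - 0.6²) = sqrt(0.34) = 0.583. Noncentrality = (0.8/0.583)×sqrt(5) = 3.07 on 17 df. Power 82%.

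The same formulas for other inputs:

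| Assumption | Group main effect | Group-by-time | Baseline-adjusted |
|---|---|---|---|
| Constant 0.8 SD, ρ = 0.4 | 47% | 32% | 77% |
| Constant 0.8 SD, ρ = 0.6 | 38% | 47% | 82% |
| Constant 0.8 SD, ρ = 0.8 | 32% | 80% | 96% |
| Effect rising 0.2, 0.4, 0.6, 0.8 SD, ρ = 0.6 | 18% | 37% | 44% |

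In the last row the five-time mean is 0.4, the sum of squared deviations is 0.4 (lambda = 5×0.4/0.4 = 5), and the post-treatment mean is 0.5.

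**Type I error of the within-subject tests.** 40,000 simulated null trials per pattern, 10 per group, tests at weeks 0, just after 0, 1, 2 and 3:

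| Assumed covariance | Epsilon | Uncorrected, group-by-time | Uncorrected, time | Greenhouse-Geisser, both tests |
|---|---|---|---|---|
| Compound symmetry | 1.00 | 5.1% | 5.2% | 3.9% |
| Subject effect + decay + noise | 0.86-0.89 | 5.6%-5.7% | 5.8% | 3.9%-4.1% |
| Strong decay, week-to-week 0.5-0.9 | 0.59-0.47 | 8.4%-9.5% | 8.3%-9.4% | 4.6%-4.9% |

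The group main effect stayed at 4.9%-5.0% throughout. Fatigue has one difference only, so sphericity cannot fail there.

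The power figures assume compound symmetry and the higher error rates assume decay. They are separate scenarios and should not be added together.

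**Missing values, if there were any.** With 5% of values missing at random, 0.95^5 = 0.774, so about 15.5 of 20 participants are complete. On the sample-size formula with m = 5, ρ = 0.5, group-effect power falls from 0.59 to 0.47; a mixed model using all available values keeps 0.585. With no missing values both give 0.59.

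**The case against.** The strongest reply is that the plan is incomplete rather than wrong. It does not say the F tests are uncorrected, and one sentence naming a correction would settle the type I error without changing the model. That stands for sphericity. It does not answer the baseline point, which follows from the five values that the plan puts into the analysis.

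Three stronger readings are tempting, and the documents do not support them.

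- **That participants and power have been lost to missing values.** A reader might infer this from "They were informed they could withdraw from the study at any point" and "Values were only accepted if the CV was less than 3" (per cent). The first is a consent statement. The second is a quality rule, and a rejected reading can be repeated. Outcome Measures reports all five test occasions as done for every participant, and the Statistical Analysis Plan counts five values each. No withdrawal or missing value is described. A rule is still needed, since attending a session does not guarantee a usable value for every variable.
- **That uneven test times break sphericity.** The condition concerns the covariance of differences, not the spacing. Under compound symmetry the spacing is irrelevant. A same-day correlation of 0.7-0.8 with weekly decay 0.5-0.8 gives 6.3%-7.3% for group-by-time, below the strong-decay figures.
- **That any mixed model cures both problems.** On complete data a random-intercept model gives the same F as the uncorrected ANOVA when the estimated intercept variance is positive. An unstructured model of the five times gave 15% type I error for group-by-time with a Wald chi-square test and 9%-9.4% with an F test on 18 df; the exact multivariate F gave 5%.

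Making baseline a covariate also removes the direct pre-to-post comparison that the plan asks for, so that comparison needs its own analysis.

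**Conclusion.** The concern holds in a limited form. As written, the plan leaves the time and group-by-time tests open to a type I error between 5% and about 9.5%, depending on a covariance that the documents do not give. The group main effect and fatigue are not exposed.

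The firmer loss is in the treatment comparison: 38% or 47% power against 82%, assuming a constant 0.8 SD post-treatment effect, correlation 0.6 and 10 per group. The ordering holds in every scenario tabulated, but the gap narrows when the effect builds up over sessions, and against group-by-time also when correlation is high. Loss from dropping incomplete participants is conditional and may be zero.

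**What to change.** For each outcome measured five times:

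- **Between-group comparison.** Model the four post-treatment values, with the pre-session-1 value as covariate and group, session and group-by-session as fixed effects. Fit by REML as a mixed model using all available post-treatment values. State the covariance structure in advance, name a fallback that does not impose compound symmetry (for example heterogeneous first-order autoregressive), and name the small-sample degrees-of-freedom method (for example Satterthwaite).
- **Pre-to-post time comparison.** Keep the ANOVA and state that Greenhouse-Geisser p-values are the ones reported.
- **Missing values.** Say what happens when a value is rejected or absent.

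The document is written in the past tense. If results have already been seen, label the change as made afterwards.

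The cost is a few sentences of SAP text and a further model to fit. An unstructured covariance over four sessions has 4×5/2 = 10 parameters to estimate from 20 participants, which is why the fallback and the degrees-of-freedom method must be named. The Greenhouse-Geisser tests are slightly conservative, at about 4%-5%.

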The licensed massage therapist worked under their own liability and performed both treatments on all participants for this study. The therapist received training to perform the spinal mobilisation intervention. This training was monitored with force plate measurements (Kistler Instruments Ltd., Force Plate Type 2875A, Hampshire, UK) until the desired force was repeatedly applied. These forces were monitored during the intervention treatment sessions to retain the same treatment as much as possible.

For the spinal mobilisation intervention, the therapist performed a 30-minute spinal mobilisation intervention (rate = 0.37Hz, 22 beats per minute, force = less than grade 1, threshold of 80N, location = L1-L5). The force for both the intervention and the massage treatment were controlled using real-time force plate data collection. The massage therapy involved a 30-minute general massage, with no specificities or consistencies. Manual contact was applied on mid-lower back; rate and force magnitude of touch was not constant. This treatment acted as an alternative therapy, allowing comparison of the specificities of the intervention, and blinding of treatment.

During the first session, the participant carried out baseline tests for myometry, balance, pain, and fatigue pre their first session for both massage and intervention sessions. The myometer, balance and pain tests were then tested post the first session. During the subsequent three sessions, the participants completed the myometer, balance and pain tests post treatment and the final fatigue test following their last session. Participants therefore completed five sets of tests for the myometer, balance and pain, to test the cumulative effect. The fatigue test was only completed pre and post all treatment sessions due to the set-up of the questionnaire. Once all testing sessions were complete, participants were thanked for their

contribution and given a debrief sheet with further information and contact details to give to their GP or carer as appropriate.

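### The pre-treatment value is analysed as an outcome rather than as a covariate and no treatment contrast is named; the group effect recovers only 80% of the mean post-treatment difference (50% for fatigue)

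*Combined protocol and SAP*

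**What the plan says.** Outcome Measures gives the testing schedule: "A total of five testing sessions were completed for each participant, pre and post session one, and post sessions two, three and four". The Statistical Analysis Plan averages the trials within each testing session, "resulting in 5 values for each variable (except fatigue"), and all five values go into the analysis. Fatigue scores were "only collected twice, pre and post all sessions, resulting in 2 values for each participant". Each outcome is then analysed in a repeated measures ANOVA with treatment group as the between-subjects factor. The only statement of purpose is "This was to determine differences between the two treatment groups and between the different time points".

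Neither the protocol sections nor the Statistical Analysis Plan mentions a covariate, a change score, an adjusted mean, a group-by-time term or a single time point for the treatment comparison. The Participants section sizes the trial for a group comparison, "The recommended number of participants for repeated measures, between factors ANOVA is 36 (18 participants in each group"), at an effect size of 0.4, power 0.8 and significance level 0.05. Recruitment ended at 20. The Procedure section gives the reason for repeated testing: "Participants therefore completed five sets of tests for the myometer, balance and pain, to test the cumulative effect".

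**The concern.** A mixed ANOVA of this kind yields three tests: group, time, and group by time. Only the first and third compare the treatments, and they answer different questions. The group effect compares the arms on the average of all occasions, including the one before treatment. Group by time asks whether the arms move differently over the occasions. The plan does not say which of these is the treatment result, and its wording matches the two main effects.

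If the group effect is taken as the treatment result, two things follow. The estimate is pulled towards zero, because one of the averaged values cannot carry a treatment effect. And stable differences between people stay in the error term, although a pre-treatment measurement that could remove much of that variance was collected. In a trial of 20, a real difference would be understated and more easily missed, and a null group effect could be misread as showing no difference between treatments.

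**Working it through.** **Inputs from the documents.** Five values per outcome, one before and four after treatment; for fatigue, one before and one after. Two randomised groups, so the expected pre-treatment difference is zero. Planned total 36, actual total 20. Effect size f = 0.4, which for two equal groups is a difference of 2 × 0.4 = 0.8 SD.

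**Assumed, because the documents give no figure.** 10 per arm, complete data, and the same correlation r between any two occasions (compound symmetry), with r from 0.3 to 0.8.

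**1. Which test the sample size serves.** With N participants and m measurements, the between-groups test has noncentrality λ = N × f² × m / (1 + (m−1)r), with 1 and N−2 degrees of freedom. The plan states neither m nor r.
- m = 3, r = 0.5: λ = 36 × 0.16 × 3 / 2 = 8.64, power 0.815. The smallest even total reaching 0.80 is 36, the plan's figure.
- m = 5 gives 36 at r = 0.6 and 32 at r = 0.5.
- For a group-by-time test, λ = N × f² × m / (1−r). The total needed is 6 to 20 for m = 2 to 5 and r = 0.3 to 0.7, so 36 does not fit.

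The sample size therefore points to the group effect.

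**2. Dilution.** With zero expected difference before treatment and mean difference D afterwards, the group effect has expectation (m−1)/m × D.
- Five values: 4/5 = 80%. A difference of 0.80 SD becomes 0.64 SD.
- Fatigue: 1/2 = 50%. A difference of 0.80 SD becomes 0.40 SD.

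A large simulation with a true difference of 0.80 gave 0.645 for the five-value group effect and 0.804 for the post-treatment values alone.

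**3. Power, worked at r = 0.5 for a constant 0.8 SD difference, n = 10 per arm.**
- Group effect: SD of the five-value mean = √((1 + 4 × 0.5)/5) = 0.775. Standardised difference 0.64/0.775 = 0.826. Noncentrality 0.826 × √(10/2) = 1.85, 18 df, power 0.42.
- Group by time: the differences (0, 0.8, 0.8, 0.8, 0.8) have squared deviations from their mean of 0.64² + 4 × 0.16² = 0.512. λ = (10/2) × 0.512/(1 − 0.5) = 5.12, 4 and 72 df, power 0.38.
- Baseline-adjusted mean of the four post values: residual SD = √((1 + 3 × 0.5)/4 − 0.5²) = 0.612. Standardised difference 0.8/0.612 = 1.306. Noncentrality 2.92, 17 df, power 0.79.

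The adjusted session-four difference and the fatigue ANCOVA use 0.8/√(1 − r²) with 17 df. Power over the range of r:

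| Setting and test | r = 0.3 | 0.5 | 0.7 | 0.8 |
|---|---|---|---|---|
| Constant effect: group | 0.53 | 0.42 | 0.34 | 0.31 |
| Constant effect: group × time | 0.28 | 0.38 | 0.60 | 0.80 |
| Constant effect: adjusted post mean | 0.78 | 0.79 | 0.88 | 0.96 |
| Linear build to 0.8 SD at session four: group | 0.25 | 0.19 | 0.16 | 0.15 |
| Linear build: group × time | 0.22 | 0.30 | 0.49 | 0.68 |
| Linear build: adjusted post mean | 0.40 | 0.41 | 0.51 | 0.63 |
| Linear build: adjusted session four | 0.42 | 0.50 | 0.66 | 0.80 |
| Fatigue: group | 0.18 | 0.17 | 0.15 | 0.15 |
| Fatigue: group × time | 0.30 | 0.40 | 0.59 | 0.76 |
| Fatigue: ANCOVA | 0.42 | 0.50 | 0.66 | 0.80 |

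For a constant effect, the group test keeps 69%, 53%, 39% and 33% of the adjusted power.

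**4. At the recommended 36.** A constant 0.8 SD post-treatment difference gives the five-value group effect power 0.80, 0.67, 0.57 and 0.53 across the same r. Without dilution the figures would be 0.94, 0.85, 0.76 and 0.72.

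**5. Simulation check, 6,000 trials per cell.** The group and group-by-time tests agreed with the formulas within 0.02. The adjusted tests ran 0.01 to 0.03 lower (constant effect: 0.75, 0.77, 0.86, 0.95). Type I error was 0.047 to 0.056 for all tests.

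**The case against.** The strongest reply is that the harm depends on one reading. The Participants section calls the design mixed factor, and the Procedure section says the repeated tests serve to examine a cumulative effect. That is naturally a group-by-time question, and the planned ANOVA produces an undiluted test of it. Keeping the pre-treatment value among the outcomes is legitimate when the contrast is change or group by time. For fatigue, group by time is simply the change-score comparison, and ANCOVA adds only 0.04 to 0.12 in power. This stands as far as it goes, but the plan never names the interaction and its sample size is for the between-groups test. For a constant effect, group by time also trails the adjusted test at every correlation shown. It overtakes the adjusted post mean only for a building effect at high correlation (0.68 against 0.63 at r = 0.8), where the adjusted session-four difference reaches 0.80.

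Second, compound symmetry may overstate the loss, since two tests fall on one day and the rest are weekly. With correlation decaying by occasion (AR(1), also an assumption) at lag-one values of 0.3, 0.5, 0.7 and 0.8, a constant effect gives group-effect power 0.66, 0.53, 0.41 and 0.36, against 0.78, 0.70, 0.68 and 0.73 adjusted. The group effect then keeps between 85% and 49% of the adjusted power. The loss is smaller but never reverses.

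Third, f = 0.4 is a generic large effect tied to no outcome or occasion. It could already describe the all-occasion average, in which case the shortfall at 36 would not arise. Nor does anything link the sample size to fatigue; the 50% follows from applying the same group effect to that outcome. Both points are fair and limit step 4, but not the 80% and 50% fractions.

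**Conclusion.** The concern holds, and the plan should be changed. Three parts rest on the text and on randomisation alone: the pre-treatment value is one of the analysed outcomes, no treatment contrast is named, and the group effect estimates 80% of the mean post-treatment difference (50% for fatigue).

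The size of the power loss depends on assumptions: 10 per arm, complete data, a 0.8 SD difference and the correlation pattern. Under compound symmetry with a constant effect, the group test loses about a third of the adjusted power at r = 0.3 and about two thirds at r = 0.8; at r = 0.1 it still keeps 85%. The loss passes one half above r of about 0.54 under compound symmetry, but only near a lag-one value of 0.8 under AR(1). If group by time is taken as the test, most of the gap closes for fatigue.

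This is a loss of precision and an ambiguity, not an invalid test. It matters because, with 20 of the recommended 36 participants, there is little power to spare.

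**What to change.** Take the value before session one out of the outcome vector and use it as a covariate.

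- **Myometry, balance, sit-to-stand and pain:** fit a linear mixed model to the four post-session values with baseline, group, session and group by session. Name the baseline-adjusted group difference as the treatment test. Report group by session and the adjusted session-four difference for the cumulative effect.
- **Fatigue:** use ANCOVA of the final score on the baseline score and group.
- **Reporting:** give adjusted differences with 95% confidence intervals. Show the planned ANOVA alongside, with its group-by-time term, and state that the adjusted analysis is a change from plan.

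The cost is one degree of freedom for the covariate and a re-analysis in the same software ("Analysis was carried out on SPSS (version 23")), with no new data. Collection and analysis are described as complete, so this is more than a wording edit. A contrast chosen after the data are known should be presented as a secondary or sensitivity analysis unless the change is openly reported.

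### The five test sets are meant to test a cumulative effect, but that term is undefined and the planned ANOVA cannot by itself tell build-up across sessions from a constant same-day change

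*Combined protocol and SAP*

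**What the plan says.** The Procedure section says that four sessions still permit a cumulative effect to be analysed, and it ties the test schedule to that aim: "Participants therefore completed five sets of tests for the myometer, balance and pain, to test the cumulative effect". Procedure and Outcome Measures both fix the occasions as before and after session 1, then after sessions 2, 3 and 4. Nothing is measured before treatment at sessions 2 to 4. Fatigue is handled separately: "The fatigue test was only completed pre and post all treatment sessions".

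The Statistical Analysis Plan reduces the data to one value per occasion, "resulting in 5 values for each variable (except fatigue) and each participant used for statistical analysis". The dependent variables "were analysed each in a between-subjects repeated measures ANOVA", and the aim is given as: "This was to determine differences between the two treatment groups and between the different time points". On presentation it says: "Analysis was carried out on SPSS (version 23) using mean values with standard error dispersion values".

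No section defines *cumulative*, and none names a contrast, a trend test or a pairwise comparison. The comparator is active. Of the massage, the Procedure section says: "This treatment acted as an alternative therapy, allowing comparison of the specificities of the intervention". There is no untreated arm.

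**The concern.** The null hypothesis of the time test is that all five means are equal. For the group-by-time test it is that the two arms have parallel profiles. Suppose each session changes the measurement by the same amount *a* and nothing accumulates. The means are then (0, *a*, *a*, *a*, *a*). This profile breaks the time null, and breaks the group-by-time null if it occurs in one arm only. So does a profile that rises from session to session. A significant F does not say which of the two occurred.

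The two obvious follow-ups have the same weakness as measures of build-up. The difference between pre-session 1 and post-session 4, and a linear trend over all five points, both include the only pre-treatment value.

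What is at stake is that the documents' own reason for testing five times goes unanswered, and that a significant time effect could be misread as accumulation.

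**Working it through.** **The plan's own figure.** The documents give no calculation for a cumulative effect. Their one sample-size figure, 36 (effect size 0.4, power 0.8, level 0.05), fits a between-groups factor under some values of inputs that are not stated: 3 measurements with correlation 0.5 (power 0.815) or 5 measurements with correlation 0.6 (power 0.807). With 5 measurements and correlation 0.5 the formula gives 32. The point here does not depend on that figure.

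**Inputs from the documents.** 20 participants, two arms, five occasions (one pre, four post), sessions on four consecutive weeks, level 0.05.

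**Assumptions not in the documents.** 10 per arm, SD 1 at every occasion, constant correlation ρ of 0.5, 0.7 or 0.8 between occasions, largest effect 0.5 SD.

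**Profiles, in SD.** SS is the sum of squared deviations of the five means from their average.
- Constant same-day change (0, .5, .5, .5, .5): SS = 0.200
- Build-up after session 1, 0.5 × (0, 0, 1/3, 2/3, 1): SS = 0.189
- Even build-up, 0.5 × (0, .25, .5, .75, 1): SS = 0.156

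**F tests.** The degrees of freedom are 4 and (20 − 2) × 4 = 72. With the effect in both arms, the time F has noncentrality 20·SS/(1 − ρ). With the effect in one arm, the group-by-time F has noncentrality 20·(1/4)·SS/(1 − ρ) = 5·SS/(1 − ρ). At ρ = 0.5 and a constant change in one arm this is 5 × 0.200/0.5 = 2.00.

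| Rejection at ρ = 0.5/0.7/0.8 | Constant change | Later build-up | Even build-up |
|---|---|---|---|
| Group-by-time F, one arm | 16/25/37% | 16/24/35% | 14/20/29% |
| Time F, both arms | 57/82/95% | 55/79/94% | 46/70/88% |

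The F rejects slightly more often without build-up than with it.

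**Single contrasts between arms, effect in one arm** (t test on a difference score, 18 df):

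| Rejection at ρ = 0.5/0.7/0.8 | Constant change | Later build-up | Even build-up |
|---|---|---|---|
| Post-4 minus pre-1 | 19/28/39% | 19/28/39% | 19/28/39% |
| Linear trend, all five points | 16/23/32% | 24/37/51% | 22/33/46% |
| Post-4 minus post-1 | 5% | 19/28/39% | 12/18/24% |
| Linear trend, post-1 to post-4 | 5% | 20/30/42% | 13/19/26% |

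Only the last two rows stay at the nominal 5% when nothing accumulates. Their merit is that they are zero under a constant response; they are not generally more powerful than the F.

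**Check at a larger effect.** In a simulation of 3,000 trials per scenario (ρ = 0.5, both arms, 1 SD), the time F rejected in 99.8% for a constant change and 98.5% for an even build-up. The post-session linear trend rejected in 5.8% and 91.7%.

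**Precision of post-4 minus post-1.** With constant correlation the SD of the difference is √(2(1 − ρ)).
- Between arms, 95% half-width = 2.101 × SD × √(2/10) = 0.94/0.73/0.59 SD.
- Within one arm, 2.262 × SD/√10 = 0.72/0.55/0.45 SD.

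These two occasions are three weeks apart. If the correlation decays weekly, ρ is replaced by ρ³ = 0.125/0.343/0.512, and the between-arm half-width becomes 1.24/1.08/0.93 SD.

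**Multiplicity.** The outcomes concerned are stiffness, tone, elasticity, sway velocity, rising index, weight transfer and pain. Seven independent tests at 0.05 would give 1 − 0.95⁷ = 30% chance of at least one false positive. Independence is doubtful, since for the myometer "The stiffness, tone and elasticity parameters are reported as a mean of these impulses".

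**The case against.** **Cumulative may mean total change.** The Procedure section uses the word when defending four sessions against the larger number it says are more likely to show benefit. That fits the total effect of a course, for which post-session 4 minus pre-session 1 is the right target. The tie to all five test sets leans towards a profile, but the text is ambiguous. This stands, and total change therefore belongs in the report beside build-up.

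**The plan does not exclude follow-up comparisons.** Its wording on time points could cover specific pairs, and it does not call the F an overall test. This stands as a point about specification. None is named, though, and without a definition even a full set of pairwise tests would not say which pair bears on accumulation.

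**Means by session would show the profile.** They would help a reader, but the plan has no estimate of build-up with an interval for the change.

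**The remedy is weak.** Between arms, post-4 minus post-1 detects an even build-up of 0.5 SD in only 12 to 24% of trials, and it cannot isolate carry-over. Both are true. The remedy offers an honest estimate and will not settle the question.

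**Stronger readings are not supported.** A reader might infer that the trial will report any time effect as cumulative; no section says so. A reader might also infer that the ANOVA is invalid, or that the data cannot address build-up. The ANOVA is a legitimate test of differences between groups and time points, and the four post-session values allow a build-up contrast.

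**Conclusion.** The point holds in a limited form. The documents give a cumulative effect as the reason for the schedule, leave it undefined, and name only an ANOVA whose significant result does not by itself show accumulation. That conclusion follows from the null hypotheses and needs no assumed numbers. The percentages and half-widths do rest on the assumed SD, correlations, effect size and 10:10 split.

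The harm is an unanswered question and a possible misreading. Fatigue, with two values, is outside the point. Since the text describes data collection and analysis as done, this is an optional exploratory addition to the analysis report, with modest priority.

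**What to change.** In the analysis report, for myometry, balance and pain only, give three quantities for each arm and as between-arm differences, each with a 95% confidence interval:

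1. Same-day change: post-session 1 minus pre-session 1.
2. Total change: post-session 4 minus pre-session 1.
3. Build-up across sessions: a contrast restricted to post-session values, either the linear trend over post-sessions 1 to 4 or post-session 4 minus post-session 1. The trend uses all four values and is slightly more powerful here (20.0% against 18.5% at correlation 0.5, later build-up). The simple difference has the advantage that 1 and 3 then add up to 2.

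State alongside them that:
- a significant overall time effect is not by itself evidence of accumulation;
- the between-arm contrast does not detect build-up common to both arms;
- within-arm change may include practice effects, as there is no untreated arm;
- the estimates are post hoc and exploratory, without multiplicity control;
- carry-over cannot be separated from a changing same-day response without pre-session values at sessions 2 to 4;
- precision is low, so an interval that includes zero does not rule accumulation out.

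The cost is a few difference scores per outcome from values already stored, plus report wording. No new data are needed. The price is 3 × 7 = 21 uncorrected between-arm estimates, which are imprecise.
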